10.9. Appendix 9: Protocol Amendment change history

The Protocol Amendment Summary of Changes Table for the current amendment is located directly before the Table of Contents (TOC).

1. INTRODUCTION

The purpose of this SAP is to describe the planned analyses to be included in the clinical study report (CSR) for study ROTA-098 (218485). Details of the planned analyses are provided.

1.1. Objectives, Estimands and Endpoints

Objectives	Endpoints**
Primary (Confirmatory)	

 To demonstrate the immunological non-inferiority of IPV when co-administered with Rotarix PCV-free compared with IPV administered alone. 	
 Anti-poliovirus types 1, 2 and 3 neutralizing Ab seroconversion rate* 1 month post Dose 3 of IPV in the Co-administration and Staggered groups.
Secondary (Descriptive)	

 To evaluate the immunogenicity of IPV when co-administered with Rotarix PCV-free and when administered alone. 	
 Anti-poliovirus types 1, 2 and 3 neutralizing Ab GMTs at 1 month post Dose 3 of IPV in the Co-administration and Staggered groups. Percentage of participants with anti-poliovirus types 1, 2 and 3 neutralizing Ab titers $\geq 1:8$ and $\geq 1:64$ at 1 month post Dose 3 of IPV in the Co-administration and Staggered groups.

 To evaluate the immunogenicity of Rotarix PCV-free when co-administered with IPV and when administered alone. 	
 Anti-RV IgA Ab seroconversion rate** 1 month post Dose 2 in the Co-administration and Staggered groups. Anti-RV IgA Ab GMCs at 1 month post Dose 2 of Rotarix PCV-free in the Co-administration and Staggered groups. Percentage of participants with anti-RV IgA Ab concentrations ≥ 90 U/mL at 1 month post Dose 2 of Rotarix PCV-free in the Co-administration and Staggered groups.

 To evaluate the reactogenicity of Rotarix PCV-free and IPV in terms of solicited systemic events. To assess the safety of Rotarix PCV-free in terms of unsolicited AEs and serious adverse events (SAEs) and safety of IPV in terms of SAEs. 	
 Solicited AEs 
 For each solicited systemic event, percentage of participants reporting the occurrence of the event within 14 days (Day 1- Day 14) after Dose 1 and Dose 2 of Rotarix and IPV Unsolicited AEs 
 Percentage of participants reporting the occurrence of unsolicited AEs within 31 days (Day 1- Day 31) after each dose of Rotarix, according to the MedDRA classification. SAEs: 
 Percentage of participants reporting SAEs from the first dose of the study intervention up to study end in the Co-administration and Staggered groups.

Ab: Antibody; GMC: Geometric mean Ab concentration; GMT: Geometric mean Ab titer; IgA: Immunoglobulin A; IPV: Inactivated poliovirus vaccine; MedDRA: Medical Dictionary for Regulatory Activities; mL: milliliter; PCV: *Porcine circovirus*; SAE: Serious Adverse Event; U: Unit

*Seroconversion rate for IPV neutralizing Ab is defined as percentage of participants with

[figure not shown]
- Titer $\geq 1:8$ at 1 month after 3 dose primary schedule of IPV in participants with titer $<1:8$ pre-vaccination
- Titer ≥ 4 -fold increase in titer 1 month after 3 dose primary vaccination schedule in participants with titer $\geq 1:8$ pre-vaccination.

Note: the 4-fold increase will take into consideration the expected decline in maternal antibodies with estimated half-life of 28 days.

**Seroconversion rate for anti-RV IgA Ab is defined as the percentage of participants who were initially seronegative (i.e., with anti-RV IgA Ab concentration <20 U/mL prior the first dose of *Rotarix*) and developed anti-RV IgA Ab concentration ≥ 20 U/mL at 1 month post Dose 2.

** complementary details on estimand including impact of intercurrent events on the analysis is available in Section 3 and Section 4.

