4.2. Scientific rationale for study design

In China, under the NIP, a 3-dose primary vaccination against poliovirus is currently recommended during the first year of life in a 2, 3 and 4 months of age schedule. *Rotarix* should be given in a 2-dose schedule between 6-24 weeks of age with an interval of at least 4 weeks between doses. Till date, there is no data available on the immunogenicity and safety of IPV when co-administered with *Rotarix* PCV-free, in healthy Chinese infants.

The current study is therefore designed to assess the immunogenicity and safety of IPV when it is co-administered with *Rotarix* PCV-free, compared to administration of the vaccines separately. There are 2 parallel arms:

- **Co-administration group:** participants will receive *Rotarix* PCV-free co-administered with IPV at Month 0.5 and Month 1.5, and IPV at Month 2.5.
- **Staggered group:** participants will receive *Rotarix* PCV-free at Day 1 and Month 1, and IPV at Month 0.5, Month 1.5, and Month 2.5.

The study will enroll infants 6-10 weeks of age. This will ensure compliance with the recommendations mentioned below, including for participants of the Co-administration group who will receive the first dose of *Rotarix* and IPV at 2 weeks after enrolment:

- As per CDC recommendation, the first dose of *Rotarix* should be given before an infant is 15 weeks of age and the second dose before they turn 8 months old.
- As per EU SmPC recommendation, the first dose of *Rotarix* may be administered from 6 weeks of age. There should be an interval of at least 4 weeks between doses. The second dose should preferably be given before 16 weeks of age but must be completed by the age of 24 weeks.
- In China, IPV is recommended as 2 doses at the age of 2 and 3 months and no later than 13 weeks of age for the first dose.

Please refer to the IB for further information on *Rotarix*.

Please refer to the PI for further information on Beijing Biological Products Institute Co.,Ltd. IPV.

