4.5. Safety Analyses

The analyses will be descriptive and conducted on the ES.

The following calculations will be performed for each group:

- The percentage of doses and participants reporting at least 1 AE (solicited or unsolicited) during the 14-day (Day 1 to Day 14) solicited follow-up period will be computed, along with exact 95% CI. The same calculations will be done for AEs (solicited or unsolicited) rated as grade 3 in intensity and for AEs leading to a medically attended visit.
- The percentage of doses over the study and the percentage of participants (by dose and over the study) reporting each individual solicited systemic event will be computed, over the 14-day (Day 1 to Day 14) solicited follow-up period, following study intervention administration, along with exact 95% CI. The same calculations will be done for each individual solicited systemic event rated as grade 3 (grade 3 or grade 4 for fever) in intensity and events leading to a medically attended visit. Temperature above specific thresholds will also be summarized with threshold defined by half degree increment.

Note: Intensity of fever will be assessed by considering the grading scales recommended by the Chinese authorities [NMPA, 2019].

- The verbatim reports of unsolicited AEs will be reviewed by a physician and will be coded according to MedDRA. Every verbatim term will be matched with the appropriate Preferred Term. The percentage of participants with unsolicited AEs occurring within 31-day (Day 1 to Day 31) follow-up period after any dose of *Rotarix* PCV-free with its exact 95% CI will be tabulated by Preferred Term. The same calculations will be done for each AE rated as grade 3 in intensity, for AEs leading to a medically attended visit and for AEs causally related to HRV as per the investigator assessment.
- The percentage of participants reporting the occurrence of SAEs (any, related, fatal, fatal related) from Dose 1 of the study intervention up to study end with its exact 95% CI will be tabulated by study group and by preferred term.
- The percentage of participants reporting the occurrence of SAEs (any, related, fatal, fatal related) within 31-day (Day 1 to Day 31) follow-up period after any dose with its exact 95% CI will be tabulated by study group and by preferred term.
- SAEs and dropouts due to AEs will be described in detail.

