4.7. Interim Analyses

No interim analysis is planned. All analyses will be conducted on final data and therefore no statistical adjustment for interim analyses is required.

The final analysis will include all data up to one month after the third dose of IPV. These analyses will include the final analysis of immunogenicity and the final analysis of solicited and unsolicited symptoms and SAEs from the first dose up to Visit 7.

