6.2.2. Assessment Window

Table 4 Intervals between study visits for Co-administration group

Interval	Optimal interval	Allowed interval range	Allowed interval during special circumstances [#]
Visit 1→Visit 2	15 days	14-18 days between study enrolment and Dose 1 of IPV and Rotarix PCV-free	14-45 days
Visit 2→Visit 4	30 days	28-36 [†] days between Dose 1 of IPV and Rotarix PCV-free and Dose 2 of IPV and Rotarix PCV-free	28-60 days
Visit 4→Visit 6	30 days	28-36 [†] days between Dose 2 of IPV and Rotarix PCV-free and Dose 3 of IPV and BS for assessment of Rotavirus Ab, IgA	28-60 days
Visit 6→Visit 7	30 days	30-36 [†] days between Dose 3 of IPV and BS for assessment of anti-poliovirus types 1, 2 and 3 Ab	30-60 days

Ab: Antibody; BS: Blood sampling; IgA: Immunoglobulin A; IPV: Inactivated poliovirus vaccine; PCV: Porcine circovirus; PCV-free: no detection of PCV-1 and PCV-2 according to the limit of detection of the tests used

[†] Participants will not be eligible for inclusion in the Per Protocol Set for immunogenicity if they make the study visit outside this interval. Interval is computed as the difference between the 2 dates of the study procedure.

[#] Refer to Section 8 of the protocol for more details on special circumstances (e.g., COVID-19 pandemic).

Table 5 Intervals between study visits for Staggered group

Interval	Optimal interval	Allowed interval range	Allowed interval during special circumstances [#]
Visit 1→Visit 2	15 days	14-18 [†] days between Dose 1 of Rotarix PCV-free and Dose 1 of IPV	14-45 days
Visit 1→Visit 3	30 days	28-36 [†] days between Dose 1 and Dose 2 of Rotarix PCV-free	28-60 days
Visit 2→Visit 4	30 days	28-36 [†] days between Dose 1 and Dose 2 of IPV	28-60 days
Visit 3→Visit 5	30 days	28-36 [†] days between Dose 2 of Rotarix PCV-free and BS for assessment of Rotavirus Ab, IgA	28-60 days
Visit 4→Visit 6	30 days	28-36 [†] days between Dose 2 and Dose 3 of IPV	28-60 days
Visit 6→Visit 7	30 days	30-36 [†] days between Dose 3 of IPV and BS for assessment of anti-poliovirus types 1, 2 and 3 Ab	30-60 days

Ab: Antibody; BS: Blood sampling; IgA: Immunoglobulin A; IPV: Inactivated poliovirus vaccine; PCV: *Porcine circovirus*; PCV-free: no detection of PCV-1 and PCV-2 according to the limit of detection of the tests used

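### The by-group SAE percentages count about 105 days in Staggered and about 90 in Co-administration, which modestly flatters Co-administration in a descriptive table

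*SAP*

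**What the plan says.** SAP section 1.1 (and Table 5 of the protocol) defines the SAE endpoint as the "Percentage of participants reporting SAEs from the first dose of the study intervention up to study end" in each group.

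SAP section 4.5 turns this into two by-group tables on the Exposed Set. The first gives SAEs "from Dose 1 of the study intervention up to study end with its exact 95% CI will be tabulated by study group". The second gives SAEs "within 31-day (Day 1 to Day 31) follow-up period after any dose with its exact 95% CI will be tabulated by study group". The unsolicited-AE item in the same list is limited to doses of Rotarix PCV-free. The SAE item is not, so IPV doses open a window too.

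SAP section 4.7 fixes the end of counting for both groups: "the final analysis of solicited and unsolicited symptoms and SAEs from the first dose up to Visit 7".

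Protocol section 4.2 gives the dosing times. In Staggered, "participants will receive *Rotarix* PCV-free at Day 1 and Month 1, and IPV at Month 0.5, Month 1.5, and Month 2.5". In Co-administration, "participants will receive *Rotarix* PCV-free co-administered with IPV at Month 0.5 and Month 1.5, and IPV at Month 2.5". SAP section 6.2.2 confirms that Co-administration gets no vaccine at Visit 1: the first interval is "14-18 days between study enrolment and Dose 1 of IPV and Rotarix PCV-free".

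Neither document plans a person-time rate, a common interval for both groups, or a caveat on unequal follow-up for SAEs.

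**The concern.** A window that opens at first dose and closes at a shared visit is longer for the group dosed first. Here that follows from the design and does not depend on dropout. A table of Day 1 to 31 after each dose might be expected to even things out. It does not, because Staggered has five dosing visits whose windows join up from Visit 1 onwards, while Co-administration has three that begin at Visit 2.

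Protocol section 4.2 states the purpose as assessing IPV given together with Rotarix PCV-free against giving the vaccines separately, so readers will set the two SAE percentages side by side. With the same risk per day, the regimen under test is expected to show the lower percentage only because it is observed for less time. The sponsor already guards against a schedule artefact elsewhere: protocol section 9.3.2 declines the between-group anti-RV IgA comparison because a difference could come from the different Rotarix schedule. The SAE tables carry no such caution.

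**Working it through.** **Inputs.** Optimal and allowed intervals come from SAP section 6.2.2, Tables 4 and 5: Visit 1 to 2, 15 days (14-18); Visit 2 to 4, 30 (28-36); Visit 4 to 6, 30 (28-36); Visit 6 to 7, 30 (30-36). Dosing visits come from protocol section 4.2: Staggered at Visits 1, 2, 3, 4 and 6; Co-administration at Visits 2, 4 and 6.

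**Check on the plan's own figure.** Visit 1 to Visit 7 = 15 + 30 + 30 + 30 = 105 days = 3.5 months of 30 days. This matches the stated duration of approximately 3.5 months per participant.

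**Table 1, first dose to Visit 7.** Staggered = Visit 1 to Visit 7. Co-administration = Visit 2 to Visit 7. The difference always equals the Visit 1 to Visit 2 interval.

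| Intervals | Staggered (days) | Co-administration (days) | Difference | Ratio |
|---|---|---|---|---|
| All minimum | 14+28+28+30 = 100 | 86 | 14 | 1.163 |
| All optimal | 105 | 90 | 15 | 1.167 |
| All maximum | 18+36+36+36 = 126 | 108 | 18 | 1.167 |

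On regular windows the gap is thus 14 to 18 days, and the excess is about 16-17% when the intervals move together. Extreme mixtures of short and long intervals widen this to 122/108 = 1.13 and 104/86 = 1.21.

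**Table 2, Day 1 to 31 after any dose.** Days covered by at least one window, cut at Visit 7, counting both end days:

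- Optimal: doses on days 0, 15, 30, 45 and 75 in Staggered cover days 0 to 105 without a break, 106 days. Doses on days 15, 45 and 75 in Co-administration cover days 15 to 105, 91 days. Difference 15.
- All minimum: 101 against 87. Difference 14.
- All maximum: 116 against 93. Difference 23, because days between doses fall outside the Co-administration windows more often.

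If the table were limited to Rotarix doses, cover would be equal (61 against 61 days at optimal intervals), but the SAE item does not say that.

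**Effect on the percentage.** The documents give no SAE rate, so the 90-day risk p is an assumption, shown over a range. With the same constant hazard in both groups, the 105-day risk is 1 - (1 - p)^(105/90).

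| Assumed 90-day risk (Co-administration) | 105-day risk (Staggered) | Ratio | Expected infants per 200 | Excess |
|---|---|---|---|---|
| 1% | 1.17% | 1.17 | 2.0 vs 2.33 | 0.3 |
| 3% | 3.49% | 1.16 | 6.0 vs 6.98 | 1.0 |
| 5% | 5.81% | 1.16 | 10.0 vs 11.62 | 1.6 |

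**After the fix.** Dividing by infant-time removes the difference in length: under the equal-hazard assumption both groups have the same expected rate per 100 infant-months.

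**The case against.** The strongest reply is that nothing in the plan rests on this comparison. The safety objective is secondary and descriptive, and it concerns each vaccine's safety. Protocol section 9.4.1 is a within-group assessment. No SAE difference, confidence interval for a difference, or test is planned. That stands: a reader might infer that the SAE table is a formal comparison with a biased conclusion, and the documents do not support that reading.

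The effect is also small beside chance. Only the expectation is higher in Staggered. With 200 infants per group, equal hazard and independent binomial counts, Staggered shows more infants with an SAE in about 46% of trials and fewer in about 34% at an assumed 1% risk; at 4% the split is about 58% to 33%. The exact interval already planned would run from 1.7% to 7.7% for 8 of 200. So a reader should not infer that Staggered will show more SAEs.

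A reader could also reach for the special-circumstances column, where a 45-day first interval with every later interval at its optimum gives 135 against 90 days, 50% more. That is a corner case. With every interval at its special maximum the figures are 225 against 180, or 25%. Neither describes the planned schedule.

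Counting from first dose is a legitimate post-exposure convention, and the earlier Rotarix start belongs to the control regimen. That argues for keeping the tables. It does not make the two percentages comparable. Detailed SAE descriptions and the separate rows for related SAEs help interpretation, but they do not adjust for length of follow-up.

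**Conclusion.** The point holds as a minor issue of presentation. On the documents' own schedule both by-group SAE percentages cover about 15 more days in Staggered at optimal intervals, which for the first-dose-to-study-end table is about 16-17% more time at risk. The day counts need no assumption beyond the stated intervals. The effect on the percentages, a ratio of about 1.16 and roughly 0.3 to 1.6 infants per 200 over assumed 90-day risks of 1% to 5%, rests on an equal, constant hazard and on rates the documents do not give. The direction modestly flatters Co-administration. The primary immunogenicity analysis and every formal conclusion are untouched.

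**What to change.** In SAP section 4.5, report SAEs per 100 infant-months from first dose to Visit 7 (or earlier exit) beside each by-group SAE percentage, on the Exposed Set, and keep both existing tables. Define numerator and denominator explicitly, for example infants with at least one SAE over infant-time to first SAE, exit or Visit 7. Label the rate's interval so that it is not read as a 31-day rate. It needs only first-dose, event and exit dates. The cost is one extra column. The rate corrects for length of follow-up only; it does not adjust for any change in risk with age.

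A second option is a Visit 1 to Visit 7 table on all randomised infants. That needs the Enrolled Set, because an infant in Co-administration lost before Visit 2 is not in the Exposed Set. It is sound only if the sponsor first confirms that SAEs from any cause before the first dose are recorded as SAEs in Co-administration. The passages pull both ways: protocol Table 1 marks SAE recording from Visit 1, but protocol section 10.3.1.2 sends conditions, signs and symptoms present before the first dose to medical history, and collection from consent is spelled out only for SAEs related to study participation or a GSK product. If early events went to medical history, this table would undercount Co-administration and reintroduce the same distortion.

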1.2. Study Design

Overview of Study Design and Key Features

Design Features	
 • Experimental design: Phase III, open-label, randomized, controlled study with 2 groups. • Duration of the study: The total duration of the study, per participant, will be approximately 3.5 months • Primary completion date: Visit 7 (Month 3.5). • Control: Active control, i.e., staggered administration of licensed IPV and Rotarix PCV-free. • Blinding: Open-label. • Data collection: Standardized electronic Case Report Form (eCRF). Solicited systemic events will be collected using a diary card. • Study groups: Refer to Figure 1 and Table 1 for an overview of the study groups.
------------------------	--

Table 1 Study groups, intervention and blinding foreseen in the study

Study groups	Number of participants	Age (Min-Max)	Study interventions	Blinding
Co-administration	200	6-10 weeks*	IPV, Rotarix PCV-free	Open-label
Staggered	200	6-10 weeks*	IPV, Rotarix PCV-free	Open-label

IPV: Inactivated poliovirus vaccine; Max: maximum; Min: minimum; PCV: *Porcine circovirus*

*6-10 weeks at the time of study enrolment.

Study intervention	Study intervention name: Inactivated Poliomyelitis Vaccine Made From Sabin Strains (Vero Cells) (IPV)	Study intervention formulation: CCI [REDACTED] CCI [REDACTED] CCI [REDACTED]	Study interventions: Rotarix PCV-free (HRV PCV-free) HRV RIX4414 CCI [REDACTED] [REDACTED] Sterile water
	Presentation: CCI [REDACTED]		
	Type: Co-administered		Study
	Product category: Combination product*		Combination product*
	Route of administration: Intramuscular		Oral
	Administration site: 
 • Location: Refer to the Pharmacy Manual for more details • Directionality: Refer to the Pharmacy Manual for more details 		NA NA

Overview of Study Design and Key Features			
	• Laterality	Refer to the Pharmacy Manual for more details	NA
	Number of doses to be administered:	3	2
	Volume to be administered by dose:	0.5 mL	1.5 mL
	Packaging and labeling:	Refer to the Pharmacy Manual for more details	Refer to the Pharmacy Manual for more details
	Manufacturer:	Beijing Biological Products Institute Co.,Ltd.	GSK
mL: milliliter; Pharmacy Manual: study procedures manual			
Study intervention Assignment	
Participants will be randomly assigned (1:1) to the 2 study groups (Co-administered and Staggered).
 
The numbering of HRV vaccine supplies will be performed at GSK, using a block scheme randomization in MATerial EXcellence, a program developed by GSK. Entire blocks will be shipped to the study centers/warehouse(s).
 
To allow GSK to take advantage of greater rates of recruitment than anticipated at individual centers in this multicenter study and to thus reduce the overall study recruitment period, an over-randomization of supplies will be prepared.
		
Interim Analysis	
No interim analysis is planned.
 
All analyses will be conducted on final data.
 
The final analysis will include all data up to one month after the third dose of IPV. These analyses will include the final analysis of immunogenicity and the final analysis of solicited and unsolicited symptoms and SAEs from the first dose up to Visit 7.
		

2. STATISTICAL HYPOTHESES

Primary objective	Null hypothesis

 To demonstrate the immunological non-inferiority of IPV when co-administered with Rotarix PCV-free compared with IPV administered alone. 	
 The difference in seroconversion rate between the Co-administration group and (minus) the Staggered group is below -10% for at least 1 of the anti-poliovirus types 1, 2 and 3 Abs.

Ab: Antibody; IPV: Inactivated poliovirus vaccine; PCV: *Porcine circovirus*

The global type I error will be 2.5%. The primary objective will be achieved if the lower limit of the 2-sided 95% CI for the group difference (Co-administration group minus Staggered group) in seroconversion rate is greater than or equal to -10% for each of the anti-poliovirus types 1, 2 and 3 antibodies.

3. ANALYSIS SETS

Table 2 Population for analyses

Analysis Set	Definition / Criteria	Analyses Evaluated
Screened	
 All participants who were screened for eligibility 	
 Study Population
Enrolled	
 All participants who entered the study (who were randomized or received study intervention or underwent a post-screening procedure) NOTE: screening failures (who never passed screening even if rescreened) and participants screened but never enrolled into the study (Met eligibility but not needed) are excluded from the Enrolled Analysis set as they did not enter the study. 	
 Study Population
Exposed	
 All participants who received at least one dose of any of the 2 study interventions. Participants will be analyzed according to the study intervention administered at dose 1. 	
 Safety
Per-Protocol (PP)	
All eligible participants from the exposed set who meet the following requirements:
 
 who received the study interventions according to their random assignment and the expected study intervention administration schedule and without intercurrent conditions* that may interfere with immunogenicity and without prohibited concomitant medication/vaccination. for anti-poliovirus types 1, 2 and 3 analyses at 1 month post Dose 3 of IPV, participants should have pre- and post-vaccination immunogenicity results for at least 1 antigen and should have complied with interval between IPV Dose 3 and the post IPV Dose 3 blood sample. for anti-RV IgA analyses at 1 month post Dose 2 of Rotarix PCV-free, participants should have pre- and post-vaccination immunogenicity results and should have complied with the interval between Rotarix Dose 2 and the post Rotarix PCV-free Dose 2 blood sample. 	
 The PP Set will be used for the immunogenicity analyses. If, in any study intervention group, the percentage of vaccinated participants with serological results excluded from the PP Set for analysis of immunogenicity is 5% or more, a second analysis based on the Exposed Set will be performed to complement the PP Set analysis.

* Immunosuppressive or immunodeficient conditions identified before Visit 7.

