7. DISCONTINUATION OF STUDY INTERVENTIONS AND PARTICIPANT DISCONTINUATION/WITHDRAWAL

7.1. Discontinuation of study interventions

‘Discontinuation’ of study interventions refers to any participant who has not received all planned doses of the study interventions. A participant who discontinued the study interventions may continue other study procedures (e.g., safety or immunogenicity), planned in the study protocol at the discretion of the investigator.

The primary reason for premature discontinuation of the study interventions will be documented on the eCRF as follows:

- AE requiring expedited reporting to GSK
- Unsolicited nonserious AE
- Solicited AE
- Protocol deviation
- Not willing to be vaccinated
- Migrated/moved from study area
- Other (specify).

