4.2.2. Between groups assessment

The asymptotic standardized 95% CI for the difference in seroconversion rate for IPV at Visit 7 between Co-administration group minus staggered group will be computed using the method of Miettinen and Nurminen [[Miettinen](#), 1985]

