4.2.3. Sensitivity analyses

If more than 5% of the ES participants with immunogenicity results after study intervention are excluded from the PPS, the confirmatory analysis will be repeated on the ES.

Within groups assessment for the PPS will be repeated by sex and study sites.

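### The conditional Exposed Set repeat of the polio analysis has no IPV-receipt condition, so by schedule it can count never-IPV infants in the Staggered arm only (minor)

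*SAP*

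**What the plan says.** **Objective and rule.** SAP section 2 tests co-administered IPV "compared with IPV administered alone". The objective is met if the lower 95% limit is "greater than or equal to -10% for each of the anti-poliovirus types 1, 2 and 3 antibodies". SAP 4.2.2 says the interval for the Visit 7 seroconversion difference "between Co-administration group minus staggered group will be computed using the method of Miettinen and Nurminen".

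**Sets.** The primary analysis uses the Per Protocol Set (SAP 4.2). Under SAP 4.2.3, if more than 5% of Exposed Set (ES) participants with post-intervention immunogenicity results are excluded from the PPS, "the confirmatory analysis will be repeated on the ES". ES membership covers "All participants who received at least one dose of any of the 2 study interventions" (SAP Table 2). Code 1030 removes participants who received no dose (SAP 6.1.3).

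**Schedule.** Staggered infants receive Rotarix "PCV-free at Day 1 and Month 1, and IPV at Month 0.5, Month 1.5, and Month 2.5" (Protocol 4.2). Co-administration infants receive nothing before Month 0.5, when both vaccines are given. Their baseline blood is drawn then (Protocol Table 8).

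**After stopping.** Under Protocol 7.1, a participant who has stopped dosing "may continue other study procedures (e.g., safety or immunogenicity") at the investigator's discretion. Protocol 7.1.1 goes further and asks that contraindicated participants be encouraged to do so. SAP 4.1.1 and 6.2.4.1 leave missing titres missing.

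**The concern.** The polio comparison concerns response to IPV, but membership of the set used for its repeat is triggered by either vaccine, and the arms meet their first vaccine at different visits. If dosing stops between Visits 1 and 2, a Staggered infant is already in the ES with a Day 1 baseline titre and no IPV. A Co-administration infant stopped in the same window is outside the ES and has no baseline.

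If the Staggered infant stays and is bled at Visit 7, nothing in SAP Table 2 or 4.2.3 keeps that titre out of the repeat. Scored as not seroconverted, it lowers the control rate and moves the difference (Co-administration minus Staggered) upward, away from -10%. The ES repeat is the only planned between-group check on the PPS conclusion, so what is at stake is its value as a warning.

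**Working it through.** **1. The plan's own figures.** Inputs (Protocol 9.7, SAP 5): 160 evaluable per arm; seroconversion 96.23%, 93.83% and 97.60%; true difference 0; margin -10%; one-sided 0.025. Exact enumeration of two binomials with the Miettinen-Nurminen score statistic gives power of 98.6%, 93.8% and 99.8%, against the stated 98.2%, 92.5% and 99.7%. These agree within 2 points. The stated overall figure follows from its parts: 1 - (0.018 + 0.075 + 0.003) = 0.904. The enrolment target is 160 / (1 - 0.20) = 200 per arm.

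**2. Who can be counted.**
- Staggered, left the study before IPV: no Visit 7 titre, no imputation, not counted.
- Staggered, never had IPV, stayed and was bled at Visit 7: in the ES with both titres. Incomplete dosing (code 1070) removes the infant from the PPS only.
- Co-administration, stopped before Visit 2: no dose, so out of the ES, and no baseline sample.

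Some stopping reasons can arise in either arm between Visits 1 and 2: refusal of vaccination (7.1), a newly met exclusion criterion, or a condition making intramuscular injection unsafe (7.1.1).

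**3. How a never-IPV infant would score.** Assume no polio vaccine outside the study. A seronegative infant would be expected to stay below 1:8. For a seropositive infant, SAP 4.2.1 decays the baseline with a 28-day half-life. Visit 1 to Visit 7 is 15 + 30 + 30 + 30 = 105 days at the optimal intervals.
- Expected remaining titre: 2^(-105/28) = 0.074 of baseline.
- Required: 4 × 0.0743 = 0.297 of baseline.
- Decay alone meets this only if 2^(-105/h) = 0.297, that is h = 105/1.75 = 60 days.

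One exception is possible. If a result below cut-off is set to half of 8, i.e. 4 (SAP 6.2.9), and that value is used in the fold-rise, it passes when baseline is at most 4/0.297 = 13.5. Hence generally, not always, a failure.

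**4. Effect of k such infants.** The documents do not give k; it is an assumption, shown from 0 to 5. The arm size of 190 is also assumed, between 160 evaluable and 200 randomised. The control rate becomes 93.83% × (190 - k)/190, a fall of 93.83/190 = 0.49 point per infant. The pass probability is for Polio 2 at a true difference of -10 points (83.83% against 93.83%).

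| k | Control rate, 190 per arm | Pass probability, k among 190 | Pass probability, k added to 160 IPV recipients |
|---|---|---|---|
| 0 | 93.83% | 2.3% | 2.4% |
| 1 | 93.34% | 3.2% | 3.3% |
| 2 | 92.84% | 4.3% | 4.4% |
| 5 | 91.36% | 9.4% | 10.2% |

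With five infants added to 160 recipients, Polio 1 and Polio 3 give 11.5% and 12.3%. All are per-type figures. Passing the repeat requires all three types, so the joint probability cannot exceed the smallest of the three.

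**The case against.** The case against giving this weight is strong, and most of it stands.

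- **The ordinary route adds nobody.** Leaving between Visits 1 and 2 yields no Visit 7 titre. Bias needs an infant who stays about three months without IPV and is bled, at the investigator's discretion.
- **The endpoint may already exclude them.** Seroconversion is defined one month after a three-dose IPV schedule, relative to status before the first dose. Without IPV neither reference point exists. This is a fair reading, but the SAP does not state it, and the between-group rule refers simply to Visit 7. The plan is silent rather than wrong.
- **Outside vaccination.** Polio vaccine is in the national programme at 2, 3 and 4 months. Code 1040 for a non-study vaccine removes an infant from the PPS, not the ES, so such an infant could stay and seroconvert.
- **The match is imperfect.** A Staggered infant stopped for a reaction to the first Rotarix dose corresponds to a Co-administration infant who already has Rotarix plus one IPV dose and remains in the ES. That infant could also fail to seroconvert and lower the other arm's rate.
- **Consequence.** The repeat complements the PPS analysis and has no decision rule of its own.

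These points limit frequency and consequence. They do not remove the asymmetry: by schedule, the definition can add never-IPV infants to the control arm only.

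**Conclusion.** The gap holds as a conditional, minor point. The text allows never-IPV Staggered infants into the ES repeat and, by schedule, has no Co-administration counterpart. Each one counted would generally lower the control rate by about 0.5 point and push the repeat towards non-inferiority; two would take the Polio 2 boundary pass probability from 2.3% to 4.3%. This rests on an assumed 190 per arm, no polio vaccine elsewhere, and scoring as non-seroconverted. With no such infants there is no effect.

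A reader might infer three stronger things that the documents do not support:
- **That the control rate is lowered.** It is lowered only if such infants exist and are bled at Visit 7. The count is not given, is probably small and may be zero.
- **That the planned 20% non-evaluable indicates how many.** That allowance covers every reason for non-evaluability, including missing samples and missed windows. Nor does it show that the repeat will be triggered, because SAP 4.2.3 counts only ES participants with immunogenicity results.
- **That the primary conclusion is at risk.** It rests on the PPS, from which these infants are excluded. The probabilities above describe the sensitivity analysis alone.

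**What to change.** Add one sentence to SAP 4.2.3, with a matching note in Table 2: the ES repeat of the polio analysis includes only ES infants with at least one documented IPV dose and with pre- and post-vaccination titres. List the Staggered infants this removes, with their titres and any non-study polio vaccine. Keep the any-vaccine ES for safety. Settle this before the titres are examined by group, since the trial is open-label.

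In the same edit, reconcile the two triggers: Table 2 says 5% or more in any group, while 4.2.3 says more than 5% of ES participants.

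The cost is one sentence, one dataset flag and one listing. There are two downsides. A few Staggered infants may leave this analysis. Co-administration infants stopped after a Rotarix reaction would remain with one IPV dose while their Staggered counterparts do not; that residual imbalance tends to lower the Co-administration rate, so it is conservative for non-inferiority.
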